5.6.1. Membrane Transport Inhibitors

A clinical drug-drug interaction study (DS8201-A-A104) fam-trastuzumab deruxtecan, an ADC that shares the same linker and payload (MAAA-1181a) as U3-1402, showed that co-administration of ritonavir (a dual inhibitor of OATP1B/CYP3A) or itraconazole (a strong CYP3A inhibitor) increased the MAAA-1181a AUC by 22% and 18%, respectively. This magnitude of increase of MAAA-1181a is not considered to indicate a clinically meaningful impact on the PK of DS-8201. Although a dedicated study with a P-glycoprotein (P-gp) inhibitor was not conducted, since itraconazole and ritonavir have been reported to be strong P-gp inhibitors³¹, the increases in exposure of MAAA-1181a (22% and 18%) can be considered as a summed impact of a strong CYP3A4 inhibitor and strong P-gp inhibitor. Therefore, the impact of a strong P-gp inhibitor alone on the exposure of MAAA-1181a is expected to be no greater than that observed for a dual inhibitor such as itraconazole or ritonavir.

Although MAAA-1181a was identified in vitro to be a substrate of the efflux transporters breast cancer resistance protein (BCRP) and multidrug resistance-associated protein-1MRP-1, no dedicated study was conducted to evaluate the effects of BCRP and MRP-1 inhibitors on the exposure of MAAA-1181a. Ritonavir has been reported to be an inhibitor of BCRP^{32,33} and MRP1³⁴, supporting the conclusion that BCRP and MRP-1 inhibitors are also unlikely to have a clinically meaningful effect on exposure of MAAA-1181a. In addition, since the expression of MRP-1 in the liver (which mediates the efflux of glucuronidated or sulfated bile salt conjugates³⁵) is low³⁶, the inhibition of MRP1 is expected to have a low impact on the exposure of MAAA-1181a.

In rats, the major excretion pathway of radiolabeled MAAA-1181a was feces via the biliary route, and the urinary excretion of MAAA-1181a is low^{37,38}. MATE2-K (which is involved in the excretion of substrates into urine) is expected to have minimal impact on the exposure of MAAA-1181a in patients.

Section 13.10 provides a link to a Food and Drug Administration list of clinical inhibitors for transporters.

5.7. Discontinuation of Study Drug

The primary reason for permanent discontinuation of U3-1402 treatment administration must be recorded. Reasons for treatment discontinuation include:

- PD per RECIST v1.1
- Clinical progression: provide date (ie, definitive clinical signs of disease progression, but a recent radiographic assessment did not meet the criteria for PD according to RECIST v1.1)
- AE (See Section 5.4)
- Death
- Pregnancy
- Withdrawal by subject (**to discontinue study drug**). NOTE: In this section, this is only withdrawal for treatment with study drug and is NOT the same thing as a complete withdrawal from the study. Discuss with the subject that they will remain in the study (ie, continue with study visits and assessments, including survival follow-up).
 - Lost to follow-up
 - Protocol violation (specify)
 - Study terminated by Sponsor
 - Other, specify (eg, Investigator discretion)

If there is evidence that the subject is receiving benefit from treatment even though the subject has met a criterion for discontinuation as listed above, the subject may remain on study treatment after discussion with and approval from the Sponsor.

Discontinued subjects will be followed for survival, either through direct contacts or by collecting public records (eg, death certificates) as allowed by local laws.

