5.4.1.3. Dose Modifications

[Table 5.2](#) provides schedule modifications for specific toxicities.

Table 5.2: Dose Modification Criteria

| | Worst Toxicity NCI-CTCAE Version 5.0 Grade (unless otherwise specified) | Schedule Modification for U3-1402 |
|---|--|---|
| General disorders and administration site conditions | | |
| Infusion related reaction (eg, same reduced rate as previous infusion) | Grade 1 Mild transient reaction; infusion interruption not indicated; intervention not indicated | If infusion related reaction (such as fever and chills, with and without nausea/vomiting, pain, headache, dizziness, dyspnea, hypotension) is observed during infusion, the rate must be reduced by 50% and subjects must be closely monitored. If no other reactions appear, the subsequent infusion rate can be resumed at the initial planned rate. |
| | Grade 2 Therapy or infusion interruption indicated but responds promptly to symptomatic treatment (eg, antihistamines, nonsteroidal anti-inflammatory drugs [NSAIDs], narcotics, intravenous [IV] injection fluids); prophylactic medications indicated for ≤ 24 hours | U3-1402 infusion must be interrupted. Symptomatic treatment (eg, antihistamines, NSAIDs, narcotics, IV fluids) administered as needed. If the event resolves or improves to Grade 1, infusion can be re-started at a 50% reduced infusion rate. Upon restart, if Grade 2 symptoms recur, no further U3-1402 must be administered at that visit. The amount of U3-1402 infused must be recorded in the eCRF. Subsequent infusions must be conducted at the 50% reduced infusion rate (ie, same reduced rate as previous infusion). |

| | Worst Toxicity NCI-CTCAE Version 5.0 Grade (unless otherwise specified) | Schedule Modification for U3-1402 |
|---|---|--|
| | Grade 3 Prolonged (eg, not rapidly responsive to symptomatic medication and/or brief interruption of infusion); recurrence of symptoms following initial improvement; hospitalization indicated for clinical sequelae Grade 4 Life-threatening consequences; urgent intervention indicated | Administration of U3-1402 must be discontinued immediately and permanently. Urgent intervention indicated. Antihistamines, steroids, epinephrine, bronchodilators, vasopressors, IV fluid therapy, oxygen inhalation etc., must be administered as clinically indicated. |

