| Respiratory, thoracic and mediastinal disorders | | |
| Pulmonary toxicity | See next rows | 
If a subject develops radiographic changes potentially consistent with ILD or an acute onset of new or worsening pulmonary or other related signs/symptoms such as dyspnea, cough or fever, rule out ILD.
 
If ILD is suspected, delay U3-1402 dosing pending further evaluation and start corticosteroid treatment promptly per consensus statement ³⁹ unless clinically contraindicated.
 
Evaluation must include CT (preferably high-resolution CT) and pulmonologist consultation (when the Investigator is not a pulmonologist). The following evaluations must also be obtained, as indicated:
 
 • Infectious disease consultation as clinically indicated • Blood culture and CBC (other blood tests could be considered as needed) • Bronchoscopy and bronchoalveolar lavage if clinically indicated and feasible • Pulmonary function tests • Pulse oximetry (SpO₂) • Arterial blood gases, as clinically indicated • Diffusing capacity of the lungs for carbon monoxide (DLCO), as clinically indicated • One blood sample collection for PK analysis as soon as ILD is suspected, if feasible • Other tests, as clinically indicated 
If a non-inflammatory/infectious etiology is confirmed by the Investigator, treat accordingly and resumption of U3-1402 may occur after discussion between the Investigator and Sponsor.
 
All events of ILD regardless of severity or seriousness will be followed until resolution including after drug discontinuation.
 |

| | Worst Toxicity NCI-CTCAE Version 5.0 Grade (unless otherwise specified) | Schedule Modification for U3-1402 |
|--|--|---|

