| | Grade 1 | 
The administration of U3-1402 must be delayed. U3-1402 can be restarted only if the event is fully resolved to Grade 0:
 
 • If resolved in \leq28 days from day of onset, maintain dose. • If resolved in $>$28 days from day of onset, reduce dose 1 level. 
Toxicity management:
 
 • Monitor and closely follow-up in 2 to 7 days for onset of clinical symptoms and pulse oximetry. • Consider follow-up imaging in 1-2 weeks (or as clinically indicated). • Consider starting systemic steroids (eg, at least 0.5 mg/kg/day prednisone or equivalent) until improvement, followed by gradual taper over at least 4 weeks. • If worsening of diagnostic observations despite initiation of corticosteroids, then follow Grade 2 guidelines (if subject is asymptomatic, then subject must still be considered as Grade 1 even if steroid treatment is given). |
| | Grade 2 | 
Permanently discontinue subject from study treatment.
 
Toxicity management:
 
 • Promptly start systemic steroids (eg, at least 1 mg/kg/day prednisone or equivalent) for a minimum of 14 days or until complete resolution of clinical symptoms and CT chest findings, followed by gradual taper over at least 4 weeks. • Monitor symptoms closely. • Re-image as clinically indicated. • If worsening or no improvement in diagnostic observations in 5 days, 
 • Consider increasing dose of steroids (eg, 2 mg/kg/day prednisone or equivalent) and administration may be switched to IV (eg, methylprednisolone). • Re-consider additional work-up for alternative etiologies as described above. • Escalate care as clinically indicated. |

| | Worst Toxicity NCI-CTCAE Version 5.0 Grade (unless otherwise specified) | Schedule Modification for U3-1402 |
|---|--|--|

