| AST or ALT increased and TBL increased | AST or ALT $\geq 3 \times \text{ULN}$ with simultaneous TBL $>2 \times \text{ULN}$ | 
Delay U3-1402 until drug-induced liver injury can be ruled out. The Investigator must consult with a gastroenterologist or hepatologist as needed, and the subject must be treated accordingly.
 
Monitor AST/ALT and TBL twice weekly until resolution or return to baseline.
 
It is strongly recommended to perform a full diagnostic workup, to exclude alternative causes such as viral or autoimmune hepatitis, alcoholic liver injury, biliary tract disorders, or hemodynamic abnormalities. Results from diagnostic workup (including, for example: INR, direct bilirubin, serologic tests for Hepatitis A, B, and C; alcohol use, ultrasound, MRI, CT scan, concomitant medication use, immunoglobulin levels, ECHO) must be recorded within the eCRF.
 
If drug-induced liver injury is ruled out, the subject must be treated accordingly, and resumption of U3-1402 may occur after discussion between the Investigator and Sponsor.
 
U3-1402 will be permanently discontinued if drug induced liver injury cannot be ruled out from diagnostic workup.
 |
| AST or ALT $> 3.0 \times \text{ULN}$ (if liver metastases are present, $>5 \times \text{ULN}$) for those subjects with known Hepatitis B and/or Hepatitis C infection at baseline | -- | 
Delay U3-1402 until reactivation of Hepatitis B and/or Hepatitis C can be ruled out.
 
Perform HBV DNA and/or HCV RNA to rule out reactivation of Hepatitis B and/or Hepatitis C, respectively.
 
Hepatologist and infectious disease consultations are recommended.
 
If reactivation of Hepatitis B and/or Hepatitis C is confirmed, permanently discontinue U3-1402.
 |
| Gastrointestinal disorders | | |
| Nausea | Grade 3 (inadequate oral caloric or fluid intake; tube feeding, TPN, or hospitalization indicated) | 
Delay U3-1402 until resolved to $\leq \text{Grade 1}$, and consider treatment with anti-emetics and/or corticosteroids as per Investigator's judgment and local/institutional guidelines, then:
 
 • If resolved to $\leq \text{Grade 1}$ in ≤ 14 days resume U3-1402; • If does not resolve to $\leq \text{Grade 1}$ in >14 days reduce U3-1402 dose by 1 level. |

| | Worst Toxicity NCI-CTCAE Version 5.0 Grade (unless otherwise specified) | Schedule Modification for U3-1402 |
|--|--|---|

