ANC = absolute neutrophil count; AST = aspartate aminotransferase; ALT = alanine aminotransferase; CBC = complete blood count; CT = computerized tomography; DNA = deoxyribonucleic acid; ECHO = echocardiogram; eCRF = electronic case report form; G-CSF = granulocyte-colony stimulating factor; HBV = hepatitis B virus; HCV = hepatitis C virus; INR = international normalized ratio; ILD = interstitial lung disease;

LVEF = left ventricular ejection fraction; MRI = magnetic resonance imaging; NCI-CTCAE = National Cancer Institute Common Terminology Criteria for Adverse Events; PK = pharmacokinetics; QTcF = QT interval corrected for heart rate using Fridericia's formula; RNA = ribonucleic acid; SpO₂ = peripheral capillary oxygen saturation; TBL = total bilirubin; TPN = total parenteral nutrition; ULN = upper limit of normal.

During study treatment, subjects who develop systolic and/or diastolic hypertension that is deemed by the Investigator to be clinically significant should receive treatment with anti-hypertensive therapy according to the Investigator's judgment and local institutional guidelines.

In addition, Investigators may consider dose reductions or discontinuations of the study drug according to the subject's condition and after discussion with Daiichi Sankyo's Medical Monitor or designee.

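### The Section 5.7 benefit exception is not limited to progression, so as worded it conflicts with the Table 5.2 rows that require stopping U3-1402, and no text says which rule prevails

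*Combined protocol and SAP*

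**What the plan says.** Section 5.7 (Discontinuation of Study Drug) gives ten reasons for permanent discontinuation. The adverse-event reason has no rule of its own and refers to Section 5.4. Pregnancy is a separate reason. After the list, a subject who appears to benefit may continue after discussion with and approval from the Sponsor: "even though the subject has met a criterion for discontinuation as listed above, the subject may remain on study treatment".

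Table 5.2 (Section 5.4.1.3) sets the action for each drug-related toxicity. For a Grade 3 or 4 infusion reaction: "Administration of U3-1402 must be discontinued immediately and permanently". For ILD of Grade 2, and again for Grade 3 and 4: "Permanently discontinue subject from study treatment". For raised aminotransferases together with raised bilirubin: "U3-1402 will be permanently discontinued if drug induced liver injury cannot be ruled out from diagnostic workup". For subjects with known hepatitis B or C at baseline: "If reactivation of Hepatitis B and/or Hepatitis C is confirmed, permanently discontinue U3-1402".

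The paragraph after the table gives further discretion in one direction only: "Investigators may consider dose reductions or discontinuations of the study drug".

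**The concern.** The two sections give different answers for the same subject. Someone who is responding and develops Grade 2 ILD must stop permanently under Table 5.2. Under Section 5.7 the same subject has met a listed criterion, shows benefit, and may stay on drug if the Sponsor agrees.

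A responding subject is the one for whom an investigator is most likely to ask to continue, so this is where the wording would be tested. Section 1.2.2 names ILD as the important identified risk and hepatotoxicity as the important potential risk. Most of the five permanent-stop rows concern the lung or the liver. With approximately 40 sites in several regions, a stopping rule for these events should have one reading.

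**Working it through.** The plan gives no figure on this point, so the check compares the texts.

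**1. Reach of the exception.** Section 5.7 lists ten reasons: progression per RECIST, clinical progression, adverse event, death, pregnancy, withdrawal by subject, loss to follow-up, protocol violation, study termination, and other. Remaining on treatment makes no sense for four of them (death, withdrawal, loss to follow-up, termination). That leaves 10 − 4 = 6 to which the clause can apply, and adverse event and pregnancy are among the six. Nothing limits it to the two progression reasons.

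**2. Table 5.2 rows that order permanent discontinuation.**

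| Row | Condition |
|---|---|
| Infusion-related reaction, Grade 3/4 | none |
| Pulmonary toxicity (ILD), Grade 2 | none |
| Pulmonary toxicity (ILD), Grade 3 and 4 | none |
| AST or ALT with TBL increased | drug-induced liver injury not ruled out |
| AST or ALT raised, known hepatitis B/C | reactivation confirmed |

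That is 5 rows, 3 unconditional and 2 dependent on work-up. None mentions benefit.

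**3. Other Table 5.2 rows that order discontinuation, without saying it is permanent.**
- By grade alone: QTc, ocular, creatinine, AST/ALT, TBL, vomiting, diarrhea/colitis, oral mucositis and other adverse events, each at Grade 4 = 9.
- Conditional: two LVEF rows after a repeat test, and TBL Grade 3 taking more than 7 days to resolve = 3.

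Total: 5 + 9 + 3 = 17. Section 5.7 is itself about permanent discontinuation, so the ambiguity covers all 17. It is sharpest in the five.

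**4. How Table 5.2 handles resumption.** Where the table allows resumption after Sponsor discussion for lung or liver events, it first requires a finding about cause. For the lung: "If a non-inflammatory/infectious etiology is confirmed by the Investigator, treat accordingly and resumption of U3-1402 may occur after discussion". For the liver: "If drug-induced liver injury is ruled out, the subject must be treated accordingly, and resumption of U3-1402 may occur after discussion". Grade 1 ILD allows a restart only after full resolution to Grade 0. Section 5.7 requires benefit, discussion and approval, but sets no condition on cause, resolution or dose level. Taken literally, continuing after Grade 2 ILD would not need the resolution that Grade 1 needs.

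**5. Search for a ranking rule.**
- Sections 3.1 and 3.1.2: treatment runs until progression, unacceptable toxicity or another Section 5.7 event. No ranking.
- Section 5.4: modifications follow the worst grade and apply to drug-related TEAEs only. Section 5.7 is not mentioned.
- Text after Table 5.2: discretion to reduce or stop, not to continue.
- Section 9.3.1 and Section 13.9: both send suspected ILD to Table 5.2. Neither mentions the exception.
- Section 13.2.5: the ILD Adjudication Committee advises the Sponsor. Section 5.7 does not require its view before a subject continues.
- Section 13.2.9: no deviations or waivers. This favours the strict reading, but a Section 5.7 approval is itself protocol text, so using it is arguably neither.

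Statements that rank Section 5.7 against Table 5.2: 0.

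**The case against.** The best defence is that the clause should be read in context. The Section 5.7 list is a list of reasons to record and includes death and loss to follow-up, so its reference back to the list cannot be fully literal. Its natural scope is progression. The adverse-event reason only points to Section 5.4, where the orders are specific and mandatory, and a specific order normally outranks a general permission. Section 13.2.9 bars waivers. The clause also speaks of remaining on treatment, whereas the protocol uses words such as resume or restart when it means dosing after a hold.

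Much of this stands. Treatment beyond progression is the likely intent, and harm would require the Sponsor to approve a request against its own table while an independent committee reviews ILD cases. That keeps the severity modest.

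It does not remove the conflict. The contextual reading is an inference that no section states, and a clause that operates once a stopping criterion has been met can equally be read as overriding it. The remain/resume distinction does not help, because a subject who remains on a drug given every three weeks receives further doses.

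**Conclusion.** The concern holds as a wording conflict. The exception is not limited to progression, it literally reaches the adverse-event and pregnancy reasons, and it contradicts Table 5.2 wherever that table requires discontinuation, most clearly in the five permanent-stop rows. It is worth fixing as a modest patient-safety correction.

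Three stronger readings are tempting, and the documents do not support them:
- A reader might infer that the protocol intends dosing to continue after serious ILD or liver injury. Nothing shows that intent. Approval is required, and Sections 9.3.1 and 13.9 both send ILD to Table 5.2.
- A reader might infer bias in ORR, DoR or adverse-event rates. The documents give no rate of these events among subjects with benefit, so no number of affected subjects can be estimated and no effect on efficacy estimates is claimed.
- A reader might infer that pregnancy also conflicts with Table 5.2. That table does not address pregnancy, so the fault there is only that the clause is too broad.

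The conclusion assumes that no document outside this protocol ranks the two rules.

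**What to change.** Add one sentence to Section 5.7: *This exception does not apply to pregnancy or to any adverse event for which Table 5.2 requires discontinuation of U3-1402; for those adverse events Table 5.2 prevails.*

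The sentence should cover every Table 5.2 discontinuation row. Naming only the five permanent-stop rows would imply that the rest can be waived, including torsade de pointes (QTc Grade 4) and Grade 4 AST/ALT or TBL. If the Sponsor wants to keep discretion for Grade 4 laboratory events in the row for other adverse events, that row should be named as the only exception.

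Discretion stays for progression per RECIST, clinical progression, adverse events not related to U3-1402 (outside Table 5.2 under Section 5.4), the 28-day delay limit in Section 5.4.1.1, and further reduction-level toxicity under Section 5.4.1.2. The cost is one sentence at the next amendment and slightly less Sponsor discretion after a Table 5.2 stopping event. No analysis or sample-size text changes.

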5.8. Subject Withdrawal/Discontinuation from the Study

5.8.1. Reasons for Withdrawal

Subjects may discontinue from the study for any of the following reasons:

- Death
- Withdrawal by subject (**from the study**). NOTE: This indicates that the subject withdraws consent and refuses to undergo any further study procedures or be followed for long-term survival.
- Lost to follow-up
- Study terminated by Sponsor
- Other, specify

If the reason for study discontinuation is the death of the subject, the options for categorizing the primary cause of death are PD or AE. If the reason of death is unknown, every effort should be made to obtain the primary cause of death. Only one AE will be recognized as the primary cause of death.

5.8.2. Withdrawal Procedures

If a subject is withdrawn from both the interventional and follow-up portions of the study:

- The Investigator will complete and report the observations as thoroughly as possible up to the date of withdrawal, including the date of last dose, date of last contact, and the reason for withdrawal.
- If consent for disclosure of future information is also withdrawn, the Sponsor may retain and continue to use any data collected before such a withdrawal of consent.
- The subject may request destruction of any samples taken and not tested, and the Investigator must document this in the site study records.
- Study site personnel may use local, regional, and national public records (in accordance with local law) to monitor vital status.

See the Schedule of Events ([Table 13.1](#)) for data to be collected at the time of study discontinuation and follow-up and for any further evaluations that need to be completed.

5.8.3. Subject Replacement

Subjects will not be replaced.

5.8.4. Subject Rescreening Procedures

The study will allow rescreening once for any subject who has failed to meet the eligibility criteria during the time of initial Screening or whose Screening window has elapsed. The Investigator will consult with the Sponsor prior to making the decision to rescreen a subject. A unique subject identification number will be assigned at the time of rescreening. The initial reason that the subject was ineligible for the initial evaluation will be recorded on the Screening Log at the site and will be entered into the clinical database. If a subject undergoes rescreening,

the subject must repeat all out-of-window assessments, as specified in the protocol (i.e., procedures performed beyond the specified window prior to Cycle 1 Day 1).

